#### **Adverse Events**

In the event of an adverse reaction, the Research Coordinator or approved representative will notify the Site Investigator and Principal Investigator. The subject will be provided appropriate treatment. In addition, the event will be reported to Pfizer and the FDA via the IIR SAE form. Participant surveys will also ask about difficulty or other reactions.

## Compensation

Subjects will be compensated \$20 via a re-loadable cash card after completing the baseline survey at the enrollment visit; \$30 upon completion of the 6-month survey; and \$40 upon completion of the 12-month survey, such that they can receive a total of \$90 if they complete all three surveys. The initial cash card will be distributed and logged by the site Research Coordinator or approved representative upon completion of the baseline questionnaire; the remaining follow-up surveys and incentives will be managed by PPFA investigators.

9

#### **Criteria for Discontinuation**

All subjects will have the option to discontinue the study at any time. A subject will be discontinued from the study by the Principal Investigator only if she is unable to be contacted. There are no anticipated events that would lead to termination of the study.

### **Data Collection & Management**

The Research Coordinator, Principal Investigator, and Data Manager who will collect, input, analyze, and otherwise handle study data, have been trained in Good Clinical Practice and HIPAA regulations. All medical records will be stored at the recruiting clinic per individual clinic protocol. All research data will be stored in locked file cabinets at the study sites. All electronic survey data will be stored on a password protected, fire-walled, secure server at PPFA. Only members of the study team will have access to this information.

### **Data Analysis**

The Principal Investigator and Data Manager have access to a secure computer with Excel, SPSS, and STATA software. Analyses will be performed on an intent-to-treat basis. We will perform descriptive analyses of demographic variables to assess the success of randomization and characterize the study population. Chi-square and t-test analyses will be used to compare proportions and mean differences between groups. The primary analysis will compare DMPA continuation rates between the intervention and control groups at 6 and 12 months. Cox proportional hazards regression analyses will be used for survival analysis. Secondary analyses will compare satisfaction scores and time/money spent on contracepting behaviors between the two groups.

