## **Additional Exploratory Questions:**

Additional exploratory questions for which we will not specify hypotheses include:

- Do implementation challenges impact a clinic's ability to provide this option to DMPA users in the future?
- Are there other potential non-safety related harms associated with self-administration of DMPA sc compared to clinic administration? (e.g., forgoing other indicated health care services like STI testing in the event of a new sexual partner)
- Do satisfaction and/or continuation outcomes differ by age group or DMPA user status (i.e., continuers, first-time initiators, past users)?

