#### STUDY DESIGN

This will be an open-label, randomized parallel group clinical trial to study DMPA sc self-administration at two Planned Parenthood affiliates serving diverse patient populations. A total of 400 female patients

requesting DMPA will be randomized to either self-administration of DMPA sc or clinic administration (usual care) in a 1:1 allocation. Subjects will be followed for one year to compare method continuation rates and satisfaction between arms. All subjects will receive reminders approximately two weeks before their next injection is due. Follow-up surveys will be conducted at 6 and 12 months via secure email, phone, text messaging, or a combination to increase response rate. Adherence will be monitored by subject self-report and study outcomes will be ascertained by self-report and medical record review.

We hypothesize higher continuation rates among self-administration users compared to those who receive in-clinic administration and have sufficient statistical power to detect an estimated 13% increase (80% power; one-sided  $\alpha$ =0.05, allowing for 15% loss-to-follow-up). We project a 57% one-year continuation rate among the clinic administration group based on the findings of the CHOICE Project in St. Louis, which also provided free contraception for one year and included adolescents (Peipert et al. 2011). We project a 70% continuation rate among the self-administration group based on similar studies described above (though slightly lower due to the inclusion of adolescents in our study). Given our primary research question, and that all prior studies suggest higher continuation among women self-administering DMPA, a one-tailed hypothesis test is appropriate.

The study will include minors (ages 15–17) due to exceedingly limited information available thus far, but will not oversample adolescents. The proposed trial will be substantially larger than previous studies and the first to have adequate statistical power to detect a clinically relevant and plausible difference between self-administration and usual care. To permit some assessment of generalizability of the results, we will also calculate overall DMPA continuation rates for all DMPA users at each participating health center at the end of the study period.

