## **Inclusion Criteria**

- Females ages 15–44
- Current or past users of DMPA or desires initiation of DMPA for contraception
- Can understand spoken and written English or Spanish
- Willing to consider/attempt DMPA self-injection
- Willing to be randomized to either self- or clinic administration of DMPA
- Do not want to become pregnant in the next 12 months
- Willing to provide contact information and to complete three surveys at baseline, 6 months, and 12 months

5

- Have consistent access to a working telephone, email, and Internet
- No contraindications to DMPA use

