## **Subject Recruitment**

Recruitment will begin in July 2015 and will continue for approximately six months until a combined total of 400 subjects have been enrolled (200 intervention; 200 control). Participants will be recruited from two Planned Parenthood affiliates: Planned Parenthood Gulf Coast (Houston, TX health center) and Planned Parenthood of Central and Greater Northern New Jersey (Elizabeth, NJ and Hackensack, NJ health centers).

Patients desiring DMPA will be invited to receive more information about the study. Patients who are already using DMPA or scheduled for a DMPA injection visit will be approached by a trained Research Coordinator or approved representative. Minors will be approached with their parent or guardian if present (see consent procedures below). Patients scheduled for a DMPA injection visit may also be introduced to the study by phone prior to their appointment. Existing DMPA users may also be introduced to the study using secure existing patient communications channels such as patient portals or message retrieval systems.

At both sites, patients who desire contraception but have not yet selected a method are typically seen by a health center assistant for contraceptive counseling prior to seeing a clinician. Women who present for a new contraception consultation may be invited into the study *only after they have decided to start DMPA*. Telling them about the study earlier may make them feel pressured to use DMPA given the free contraception and compensation they would receive and reduce the generalizability of study findings. Women choosing to initiate DMPA will be approached by the Research Coordinator. This may occur in counseling or exam rooms depending on clinic flow.

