### Randomization and Assignment

Subjects who consent to participate will then be randomized to self-administration or standard clinic administration in a 1:1 allocation as follows. Before the study begins, the sequence for 1:1 group allocation will be predetermined stratified by study site. Separate randomization sequences will be generated for each site using randomly permuted number blocks.

Group assignments will be placed in sealed opaque envelopes and will be maintained by the Research Coordinator. The envelopes will be opened by the Research Coordinator or approved representative only after participant enrollment and informed consent. Study staff will complete and sign a Randomization Form for each randomized subject (See Appendix).

Crossover will be permitted from the self-administration arm to the clinic administration arm only. Any subject crossover will be documented by the Research Coordinator or approved representative with the subjects' ID number to permit later assessment of crossover and ITT analyses.

Due to the nature of the study, no blinding will be used.

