All subjects will complete an electronic baseline survey in the clinic (using tablets provided by the study) assessing demographics, sexual activity, reproductive history, and contraceptive use and satisfaction. Subject contact information will be collected for each participant including home, work, and mobile telephone numbers; home address; e-mail; and an alternate person to contact if they cannot be reached after several attempts. This information will be used for reminders and to contact the subject for follow-up surveys at 6 and 12 months following enrollment. After completing the survey, subjects will receive a re-loadable cash card (See Compensation section below).

8

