#### **Number of Subjects and Statistical Power**

The study sites will enroll a combined total N of 400 women. Individuals will be randomized to self-administration or clinic administration with a 1:1 allocation, such that 200 women will be randomized to self-injection, and 200 women to clinic administration. A 15% loss to follow-up rate will yield completed surveys from approximately 340 participants. Based on previous studies, we hypothesize greater continuation rates among self-injection users compared to patients who receive standard care and have sufficient statistical power to detect a difference of 13% or greater. While we will ask subjects about unintended pregnancies, given the high efficacy of DMPA, we will not have statistical power detect a difference between groups.

Given the primary study hypothesis that increased accessibility to DMPA through self-administration will result in higher method continuation rates and the results of prior studies, we estimate that the intervention group will have a 70% continuation rate at 12 months and the control group a 57% continuation rate. With a one-sided  $\alpha$ =0.05 and a  $\beta$ =0.80 and accounting for an approximately 15% dropout rate, completed follow-up from 338 subjects will be sufficient to detect the hypothesized difference. The study is not designed to detect statistically significant differences between adolescents and adults, or between method initiators and continuers.

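### Randomisation is stratified by site, but the comparison of proportions is an unadjusted chi-square that uses neither site nor DMPA user status: valid, with a little precision given up

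*Combined protocol and SAP*

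**What the plan says.** - **Randomization and Assignment:** allocation is 1:1 and stratified by study site. "Separate randomization sequences will be generated for each site using randomly permuted number blocks". No other stratification factor is named.
- **Data Analysis:** "Chi-square and t-test analyses will be used to compare proportions and mean differences between groups". The sentence on the primary analysis names the comparison (continuation by arm at 6 and 12 months) but no test. Cox regression is named for survival analysis. No site term, stratum or covariate is given for any method.
- **Inclusion Criteria:** the population mixes levels of experience with the method: "Current or past users of DMPA or desires initiation of DMPA for contraception".
- **Study Procedures:** the baseline survey covers what is needed to classify user status, "assessing demographics, sexual activity, reproductive history, and contraceptive use and satisfaction".
- **Additional Exploratory Questions:** whether continuation varies with age group or prior DMPA use is listed as an exploratory question without a hypothesis.
- **Number of Subjects and Statistical Power:** "completed follow-up from 338 subjects will be sufficient to detect the hypothesized difference", for 70% against 57% at a one-sided 5% level.
- **Subject Recruitment:** two affiliates are named but three health centers (Houston, Elizabeth and Hackensack). That section speaks of both sites, while the section on consent for minors uses the plural for New Jersey alone. The unit meant by *site* in the randomisation is not stated.

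**The concern.** When allocation is balanced within site, the between-site part of the outcome variance cannot contribute to the treatment difference. A plain chi-square still counts it as noise, so its standard error is slightly too large if continuation differs by site. User status is a different case. It is not balanced by design, so the plain standard error correctly includes its chance imbalance, but adjustment would remove that part of the variance.

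In both cases the consequence is lost precision, not bias or a false-positive problem. It deserves a line because the design has almost no slack (about 340 completers expected, 338 required) and because covariate adjustment carries weight only if it is fixed before outcome data are seen.

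**Working it through.** **Inputs from the protocol.** Continuation 57% (clinic) and 70% (self); one-sided α = 0.05 (z = 1.645); power 80% (z = 0.842); 400 randomised 1:1; 15% loss, so about 340 completers or 170 per arm.

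**Assumptions (not in the documents).** Gaps in continuation between sites and between user-status groups; a 40/20/40 mix of user status; equal-sized sites; permuted blocks of 4; the same 13-point effect in every stratum.

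**1. The plan's own figure.** Pooled mean 0.635.

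n per arm = [1.645·√(2·0.635·0.365) + 0.842·√(0.57·0.43 + 0.70·0.30)]² / 0.13² = 168.5, so 169 per arm and 338 in total. Then 338/0.85 = 398, consistent with 400. The stated 338 is therefore the unadjusted, pooled, one-sided size without continuity correction. At 170 per arm, power is 80.3% with the pooled null variance and 80.7% with the unpooled formula. There is no shortfall.

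**2. Ignoring site.** Two equal sites at 57% ± g/2 under the null. Ratio of within-site to total variance = (0.2451 − (g/2)²)/0.2451. True α of the plain test = 1 − Φ(1.645/√ratio).

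- g = 10 points: ratio 0.990, α = 4.91%.
- g = 20 points: ratio 0.959, α = 4.65%.

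A separate simulation of site alone (169 per arm, two equal strata, 200,000 runs) agrees in direction. Power for the plain against the site-stratified test is 80.4% and 80.4% at a 10-point gap, 80.9% and 81.5% at 20, and 81.5% and 83.8% at 30.

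**3. Adjusting for user status.** Strata at 57% − g/2, 57% and 57% + g/2, with 13 points added in the self arm. Between-stratum variance = 0.8·(g/2)². Ratio = 1 − 2·0.8·(g/2)²/0.4551, where 0.4551 = 0.2451 + 0.2100. SE = √(0.4551·ratio/170). Power = Φ(0.13/SE − 1.645).

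| Gap (points) | Variance ratio | SE (points) | Power |
|---|---|---|---|
| 0 | 1.000 | 5.17 | 80.7% |
| 10 | 0.991 | 5.15 | 81.0% |
| 24 | 0.949 | 5.04 | 82.5% |
| 34 | 0.898 | 4.90 | 84.3% |

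Chance imbalance in the share of continuers has SD √(2·0.4·0.6/170) = 5.3 points. One SD moves the estimate by 0.053 × 10 = 0.5 points at a 10-point gap and 0.053 × 24 = 1.3 points at a 24-point gap, about 10% and 25% of one SE. That is ordinary sampling error.

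**4. Both factors together, by simulation.** N = 340, 40,000 runs per case, one-sided 5%. The Monte Carlo SE is about 0.2 points per figure.

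| Assumed gaps (site / status) | Sites | Plain chi-square | Main-effects logistic (score test) | CMH over all site-by-status cells |
|---|---|---|---|---|
| 0 / 0 | 2 | 80.8 | 80.7 | 80.2 |
| 0 / 0 | 3 | 81.0 | 80.9 | 80.1 |
| 10 / 10 | 2 | 80.6 | 81.1 | 80.5 |
| 10 / 10 | 3 | 80.8 | 81.2 | 80.7 |
| 20 / 24 | 2 | 80.9 | 83.6 | 83.2 |
| 20 / 24 | 3 | 80.7 | 83.3 | 82.5 |

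Null rejection was 4.7% to 5.3% for all three tests. The logistic model changes power by −0.1, then +0.4 to +0.5, then +2.6 to +2.7 points. The Cochran-Mantel-Haenszel (CMH) test over every cell loses 0.6 to 0.9 points with no gaps, is about level at 10-point gaps, and gains 1.8 to 2.3 at the largest.

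**The case against.** The strongest reply is that this is a preference and not a defect. The plain test is valid, errs on the conservative side, matches the sample size and reaches 80% power. Every gap used to show a benefit is assumed. The largest gain needs a 20-point site gap and a 24-point status gap at once. Site alone gains nothing at 10 points and 0.6 at 20. All of that stands, and it is why the point is optional.

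Three narrower objections also have weight:

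- User status is not absent from the plan, since it is an exploratory question. It is absent only from the stated between-arm comparison, and an exploratory subgroup look does not sharpen that comparison.
- The CMH alternative is not equivalent to the logistic model. By the figures above it helps only when gaps are large.
- The simulation evaluated the logistic score test. The interval for a standardised risk difference and a site-stratified Cox model were not evaluated.

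The inference that chi-square is the primary test is also a reading, because the primary-analysis sentence names no test. The reproduced 338 supports that reading. None of this removes the case for a change that costs about 0.1 power points at worst in these simulations.

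**Conclusion.** The point holds as a minor, optional improvement. The plan stratifies by site and enrols women with differing DMPA experience, yet the only test it names for proportions uses neither fact. Validity and the stated 80% power are not in question.

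The likely gain is 0 to 0.5 power points if continuation differs by 10 points or less between sites and between user groups, and about 2.6 to 2.7 points if the gaps are 20 and 24 points. These figures rest on the assumed gaps, the 40/20/40 mix, equal sites and a constant 13-point effect, none of which the documents supply. The undefined unit of *site* has no bearing on the plain test, but any site-adjusted analysis needs it settled.

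**What to change.** Before outcome data are seen, add one or two sentences to Data Analysis:

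- **Primary 12-month comparison:** a logistic model with treatment, randomisation site and baseline DMPA user status (current, past, new) as main effects. Keep the stated one-sided level and take the test from the treatment term. Report a standardised risk difference with its interval method named.
- **Site:** define it by the same units as the randomisation lists, whether two affiliates or three health centers.
- **Sensitivity analysis:** the unadjusted chi-square.
- **Cox model:** stratify by site.

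A Mantel-Haenszel risk difference with a CMH test over site by user status is a second choice. It has 6 to 9 cells, which must not be sparse, and it loses a little power when gaps are small.

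Age group is a possible further covariate, because Study Design sets the self-administration projection "slightly lower due to the inclusion of adolescents in our study". Adolescents are not oversampled, so the gain is probably small. If 10% are adolescents with a 20-point gap (both assumed), it is 0.1·0.9·0.2²/0.2451, or about 1.5% of the variance.

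The cost is the wording alone. Site is known, the baseline survey covers contraceptive use, the named software (STATA, SPSS) fits the model, and the 400 does not change.

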# **Objectives and Hypotheses**

The primary study objective is to compare one-year method continuation rates between patients who self-administer DMPA sc outside of the clinic setting and those who receive in-clinic administration of DMPA sc. Secondary objectives are to: confirm the feasibility and acceptability of self-injection among adult and adolescent DMPA users; compare method satisfaction rates between patients who self-administer and those who receive in-clinic injections; and compare costs associated with contraceptive care across both groups.

Primary study outcome: DMPA sc continuation at one year by self-report in both the self- and clinic administration arms.

Secondary study outcomes: Patient-reported satisfaction with treatment; satisfaction with home use; cost differentials.

Primary research question: Will allowing for self-administration of DMPA sc outside of the clinic setting result in increased method continuation rates at 6 and 12 months?

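### Follow-up satisfaction is compared without adjusting for site, DMPA user status or baseline satisfaction: valid, but possibly less precise than the collected data allow

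*Combined protocol and SAP*

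**What the plan says.** The Data Analysis section gives one general sentence on between-arm methods: "Chi-square and t-test analyses will be used to compare proportions and mean differences between groups". It adds: "Secondary analyses will compare satisfaction scores and time/money spent on contracepting behaviors between the two groups". It names no covariate for any analysis, and mentions Cox regression only for survival analysis.

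Objectives and Hypotheses lists the secondary outcomes without ranking them: "Patient-reported satisfaction with treatment; satisfaction with home use; cost differentials". The objective in that section speaks of satisfaction rates, whereas Data Analysis speaks of scores. No scale or time point is given for the comparison.

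Three other sections bear on what could be adjusted for:

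- Randomization and Assignment stratifies by study site, with a separate sequence for each.
- Inclusion Criteria admits "Current or past users of DMPA or desires initiation of DMPA for contraception". Additional Exploratory Questions asks whether satisfaction differs between continuers, first-time initiators and past users.
- Study Procedures has every participant complete a baseline survey "assessing demographics, sexual activity, reproductive history, and contraceptive use and satisfaction". It does not say that the satisfaction item concerns DMPA, that it matches the follow-up item, or that it is answered before assignment is known.

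**The concern.** The plan collects a satisfaction measure at enrolment and treats user status as possibly related to satisfaction, but the only comparison it describes uses neither. It also leaves out the randomisation stratum. If these variables predict follow-up satisfaction, an adjusted comparison has a smaller standard error for the same number of women. What is at stake is the width of the interval for a named secondary outcome. There is a smaller point about credibility: in an open-label trial, covariates chosen after the results are seen are open to challenge, so any adjustment should be fixed in advance.

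**Working it through.** **1. The plan's own figure.** Number of Subjects and Statistical Power sizes the trial for continuation only. It assumes that "the intervention group will have a 70% continuation rate at 12 months and the control group a 57% continuation rate", states "With a one-sided $\alpha$ =0.05 and a $\beta$ =0.80", and allocates so that "200 women will be randomized to self-injection, and 200 women to clinic administration". With pooled variance under the null and no continuity correction:

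n per arm = [1.645 × √(2 × 0.635 × 0.365) + 0.842 × √(0.57 × 0.43 + 0.70 × 0.30)]² / 0.13² = 168.5, rounded up to 169.

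That gives 338 completers, as stated (the printed β of 0.80 is the power). Then 338 / 0.85 = 398, consistent with enrolling 400. The plan states no standard deviation, effect or power for satisfaction, so there is no figure of its own to reproduce there.

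**2. Precision of the unadjusted comparison of means.** Take 170 per arm, that is 400 × 0.85 = 340 expected completed surveys. The difference detectable with 80% power is (z for α + 0.842) × √(2/170) standard deviations (SD):

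- two-sided 0.05: (1.960 + 0.842) × 0.1085 = 0.304 SD
- one-sided 0.05: (1.645 + 0.842) × 0.1085 = 0.270 SD

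The plan does not say which applies to satisfaction.

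**3. Effect of adjusting for a baseline score held by every woman.** Residual variance falls by r², where r is the baseline-to-follow-up correlation. The equivalent number is 340 / (1 − r²), and the detectable difference is multiplied by √(1 − r²). The documents give no r, so the values below are assumptions.

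| r | Variance reduction | Equivalent n | Detectable, two-sided (SD) | Detectable, one-sided (SD) | Two-sided power at 0.304 SD |
|---|---|---|---|---|---|
| 0 | 0% | 340 | 0.304 | 0.270 | 80.0% |
| 0.1 | 1% | 343 | 0.302 | 0.268 | 80.4% |
| 0.3 | 9% | 374 | 0.290 | 0.257 | 83.6% |
| 0.5 | 25% | 453 | 0.263 | 0.234 | 89.9% |
| 0.6 | 36% | 531 | 0.243 | 0.216 | 93.8% |

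**4. Baseline score usable in only a share q of women.** With user status in the model and the baseline score set to a constant where it does not apply, variance falls by about q × r². This takes the outcome variance to be similar in the two groups and counts nothing for user status itself. The share is also an assumption, since the documents give no mix of user types.

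- q = 0.3: 2.7% at r = 0.3; 7.5% at r = 0.5
- q = 0.5: 4.5% at r = 0.3; 12.5% at r = 0.5
- q = 0.7: 6.3% at r = 0.3; 17.5% at r = 0.5

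The further gain from site and user status cannot be sized, because the documents do not say how much of the variation in satisfaction they explain.

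**5. Timing.** Randomization and Assignment has consenting women randomised and the envelope opened. Study Procedures then describes teaching and injection, and only afterwards the baseline survey. No sentence places the survey before the envelope. Site and prior DMPA use are settled before assignment whatever the order of the visit; a satisfaction rating is not.

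**The case against.** The strongest reply is that this is a preference about efficiency, since an unadjusted comparison in a randomised trial is valid. That stands. A reader might infer that chance imbalance in user status biases the result. It does not, because such imbalance is already allowed for in the standard error.

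A reader might also infer that the trial is known to lose a large share of its precision, with 340 completers worth as many as 531 under adjustment. The documents do not support this. The upper figure needs a correlation of 0.6 and a usable score from every woman, and neither is documented. The baseline item concerns contraception in general, and a first-time user cannot yet rate DMPA. Nor is 340 a stated denominator for satisfaction with treatment: the plan projects that 30% and 43% of the two arms will have discontinued by 12 months. The percentage reductions do not depend on that number, but the equivalent sample sizes do.

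The t-test is not tied to satisfaction by name. If satisfaction is analysed as a rate, the chi-square test applies and the r² arithmetic does not carry over directly. The plan would still be unadjusted.

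The most serious objection is that a satisfaction rating given after assignment is known, in an open-label trial, could be influenced by arm. Adjusting for it could then introduce bias that the unadjusted test avoids. This also stands, and it makes the fix conditional. The lack of a comparable score for first-time users does not rule out adjustment. With user status in the model and a constant in place of the score, the arm comparison remains valid provided the covariates precede assignment. What shrinks is the gain.

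**Conclusion.** The point holds as one of efficiency and prespecification. The satisfaction comparison is planned without the randomisation stratum, user status or the baseline item, and may therefore be less precise than it could be. The size is uncertain: a 1% to 36% reduction in variance for assumed correlations of 0.1 to 0.6 with a complete baseline, and about 4.5% to 12.5% at 0.3 to 0.5 if half the women have a usable score. At the low end the gain is negligible.

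A reader might go further and call satisfaction the main secondary outcome; the documents rank none. Satisfaction with home use is outside the point, since it has no baseline value and no natural counterpart in the clinic arm. The primary outcome, the 338 completers and the enrolment of 400 are unaffected.

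**What to change.** State the scale and time point for satisfaction with treatment, whether it is analysed as a score or a proportion, and whether the baseline survey asks the same item. Then prespecify a comparison by arm as randomised, adjusted for:

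- site, as used in the randomisation lists;
- DMPA user status at enrolment (continuer, past user, first-time);
- baseline satisfaction where it applies, set to a constant where it does not, with user status kept in the model.

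Use linear regression for a score, or a covariate-adjusted risk difference for a proportion.

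Include baseline satisfaction only if the survey is completed before the envelope is opened. If that order cannot be assured, adjust for site and user status alone.

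The cost is a few sentences in the analysis plan and, if baseline satisfaction is used, a small change in the order of procedures at the enrolment visit. No new data are needed, and the listed software can fit these models.
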